3.4.2 Secondary objectives

Secondary objectives are

- To assess the safety (any solicited and unsolicited AEs, laboratory assessments) of nOPV2 candidate 1 and nOPV2 candidate 2 in healthy OPV-vaccinated adults, compared with historical controls given Sabin OPV2 (study UAM1);
- To assess the safety (any solicited and unsolicited AEs, laboratory assessments) of nOPV2 candidate 1 and nOPV2 candidate 2 in healthy IPV-only vaccinated adults, compared with placebo;
- To compare the immunogenicity (seroconversion rate, median antibody titer (post-vaccination)) of nOPV2 candidate 1 and nOPV2 candidate 2 in healthy OPV-vaccinated adults, with historical control of Sabin OPV2 (study UAM1);
 - **Seroconversion** is defined as a change from seronegative to seropositive and neutralizing antibody titers of $\geq 1:8$, and in seropositive subjects, as an antibody titer increase of ≥ 4 fold over baseline titers.
- To assess the immunogenicity (seroprotection rate, seroconversion rate, median post-vaccination antibody titer) of nOPV2 candidate 1 and nOPV2 candidate 2 in healthy IPV-only vaccinated adults.

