5.1 General Principles

The study UAM1, conducted in a pre-OPV2 cessation period (2015-2016), was specifically designed to provide active control comparator data for both safety and immunogenicity for the OPV-vaccinated adults given the novel vaccine candidates in this study. For all endpoints for OPV-vaccinated subjects, summaries of data from this study will be presented alongside corresponding summaries from UAM1. Summaries of data from IPV-vaccinated subjects will be presented according to group (each candidate, and placebo), and have no historical control companion groups. Summaries of demographics, baseline characteristics, and immunogenicity data from this study will be prepared by site and overall, to assess comparability of sites. For OPV-vaccinated subjects, comparative analyses will be limited to comparison of each vaccine to the UAM1 Sabin 2 control; for IPV-vaccinated subjects, each candidate vaccine group will be compared to the placebo group for safety endpoints.

All data will be summarized and/or listed. Unless otherwise specified in this document, a two-sided type I error rate of alpha = 0.05 will be used for inferential methods, such as for the generation of confidence intervals.

Unless otherwise specified, descriptive statistics (n, mean, median, standard deviation, minimum, maximum) will be used to describe continuous variables, and frequencies and percentages will be used to describe categorical variables.

Statistical analyses will be generated using SAS®, version 9.4 or above.

Unless otherwise specified, tables will include presentation of results by time point and by group, and overall, when possible. Figures and tables which provide more than summary statistics may include neutral explanatory text to aid in their description of the underlying data.

Unless otherwise noted, “baseline” will refer to the day of first vaccination for all participants in all groups.

To the extent possible, unintended differences in terms collected on CRFs between the two studies will be aligned for summary and presentation, with any recoding of UAM1 terms clearly specified in the study report. Coded terms will use a common coding dictionary across the two studies.

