Probable – suggests that a reasonable temporal sequence of the AE with vaccine administration exists and, in the Investigator's clinical judgment, it is likely that a causal relationship exists between the vaccine administration and the AE, and other conditions (concurrent illness, progression or expression of the disease state, or concomitant medication reactions) do not appear to explain the AE.

Throughout, when the word “related” is used to refer to adverse events, it is to be understood to refer to those events considered either possible or probable.

All AEs will be summarized by type, seriousness, severity, causality, by group and overall. AEs will be summarized with tables at the subject level, where a subject contributes to the total once under the maximum severity/relationship of the event type. An adverse event summary table will be prepared summarizing the number of subjects with any unsolicited AE (and by maximum severity and by maximum relationship), any SAE by type and by maximum relationship, any related SAE, any severe unsolicited AE by maximum relationship, any serious or severe AE, any AEs leading to study/treatment withdrawal, any grade ≥ 2 unsolicited AE, and any solicited AEs by maximum severity. All adverse events will be presented in a listing, and separate summaries and listings will be developed for AE categories of special interest, as described below.

All summaries of unsolicited adverse events will present the number and percentage with a qualifying event, including a two-sided 95% exact confidence interval for the proportion, as well as the total number of qualifying events. Summaries of solicited adverse events will be summarized similarly but will omit the total event count.

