6.5.1 Primary Safety Endpoints

- Solicited adverse events:
 - Serious/severe solicited adverse events will be summarized by group, by post-vaccination time period as well as overall (under maximum severity), and by term by post-vaccination time period as well as overall (under maximum severity), as well as listed.
- Unsolicited adverse events:
 - Serious/severe unsolicited AEs will be summarized by group, maximum causality and by class (serious vs severe) under maximum causality, by post-vaccination

time period (prior to dose 2 vs following dose 2) as well as overall, and reasons for SAE classification (wherever such subcategories are relevant), as well as by SOC and PT among serious events only (and among those serious and related), and among severe events only (and among those severe and related). These events will also be listed.

- Listings will be prepared for those subjects who died or withdrew from the study due to an AE.

Two-sided p-values from the Fisher exact test of the number of subjects with an event will be presented for:

- Severe solicited events (overall, and by event term)
- Any serious unsolicited event
- Any serious and related unsolicited event
- Any severe unsolicited event
- Any severe and related unsolicited event

These comparisons will be conducted for the following groups:

- UAM4 Groups 1 & 2 vs UAM1 Groups 1 & 2
 - Post-dose-1 and overall, TVP
- UAM4 Group 2 vs UAM1 Group 2
 - Post-dose-2, TVP subjects who received both doses
- UAM4 Groups 3 & 4 vs UAM1 Groups 1 & 2
 - Post-dose-1 and overall, TVP
- UAM4 Group 4 vs UAM1 Group 2
 - Post-dose-2, TVP subjects who received both doses
- UAM4 Group 5 vs UAM4 Group 7
 - Post-dose-1, post-dose-2, and overall, TVP
- UAM4 Group 6 vs UAM4 Group 7
 - Post-dose-1, post-dose-2, and overall, TVP

Comparisons for both solicited and unsolicited events will be conducted separately for post-dose-1 and post-dose 2, as well as following any dose. Comparisons involving post-dose-2 data will include only subjects receiving both doses.

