6.5.2 Secondary Safety Endpoints

- Solicited AEs, collected within 7 days following vaccination, will be summarized by group overall and by term, (any event regardless of severity, and by severity according to maximum severity, across terms and for each term), for each post-vaccination time period as well as overall, as well as listed.
- Unsolicited AEs will be summarized by group, by relationship under maximum causality, by severity under maximum severity, by post-vaccination time period as well as overall, as well as by SOC and PT, and by SOC and severity (maximum severity). Separate tables by SOC and PT will be produced for moderate or greater events, and for moderate or greater related events only. A table will be produced summarizing preferred terms for those terms arising in >2% of subjects, sorted in descending order.
- A listing of AEs including verbatim term, start/stop date, timing (post-dose 1 vs post-dose 2), including post-prior-vaccination onset day, coded terms, severity, causality, actions taken, outcomes, and type (solicited vs. unsolicited) will be provided.

Clinical laboratory test values will be evaluated according to Common Terminology Criteria for Adverse Events (CTCAE) version 4.03 (toxicity grades using ranges for laboratory abnormalities) or in accordance with the normal ranges of the clinical laboratory (below, within, or above normal range) for parameters for which no toxicity grades are defined. The limits of quantitation will be substituted for the actual value, where necessary.

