Clinical laboratory abnormalities will be summarized by lab parameter, time point and grade (with separate categories for high and for low values of a given lab value, where relevant), as well as in a shift table displaying the frequency of post-baseline abnormalities by grade for each time point cross-tabulated with the classification at baseline, for each time point for each lab parameter, maximum grade across lab parameter within each time point, and maximum grade across post-baseline time points and lab parameter. A separate table will summarize according to grade only those values considered to be clinically relevant. Additional summary tables will be produced including the continuous values and the change from baseline for each group and post-vaccination day. Boxplots will display the raw value by lab parameter and study collection day, and will include separate symbols to depict values out of range and those out of range and clinically relevant. A listing, including grade and clinical relevance, will also be prepared.

While all safety lab abnormalities will be summarized, for each of the specific safety lab parameters listed below, the rate of moderate or greater post-baseline abnormalities will be presented at the subject level overall as well as by timepoint, and by abnormality grade (using the maximum grade post-baseline, where relevant), and accompanied by a two-sided 90% confidence interval using the Miettinen and Nurminen method for the risk difference of each vaccine candidate vs. the comparator group: ALT, AST, CK, GGT, bilirubin and albumin. For IPV-vaccinated subjects (Groups 5 and 6), comparisons will be made relative to the placebo

group (Group 7), and for OPV-vaccinated subjects (Groups 1 – 4), comparisons will be made relative to the corresponding UAM1 control (for lab values assessed in both studies), combining groups where possible, as described above (e.g., Group 1 & 2, post-dose-1).

Pregnancy test results will be listed.

Abnormal vital signs (heart rate, systolic/diastolic blood pressure, body temperature) will be summarized by group and by time point (day, prior to/following vaccination). The summary will also include the number and percent of subjects with abnormal and clinically relevant vital signs. Vital signs will be listed, and summarized as continuous variables by time point, including change from baseline, by group, and change pre- to post-vaccination for vaccination visits.

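### Any-grade adverse events in the randomised IPV groups have no planned between-arm estimate against placebo, although the laboratory part of the same secondary objective has one

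*SAP*

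**What the plan says.** SAP 3.4.2 sets a secondary safety objective that covers "any solicited and unsolicited AEs, laboratory assessments" for both candidates "in healthy IPV-only vaccinated adults, compared with placebo"; Protocol 2.2 carries the same objective. SAP 5.1 adds a general commitment: "for IPV-vaccinated subjects, each candidate vaccine group will be compared to the placebo group for safety endpoints". It names no method.

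The methods in SAP 6.5 differ by type of outcome:

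- **Any-grade solicited AEs (6.5.2):** "Solicited AEs, collected within 7 days following vaccination, will be summarized by group overall and by term", by severity and by post-vaccination period.
- **Any-grade unsolicited AEs (6.5.2):** summaries by group, relationship, severity, period and coded term. Under 6.5 these show a number and percentage "including a two-sided 95% exact confidence interval for the proportion". Solicited AEs are handled in the same way, without the event count.
- **Serious and severe AEs (6.5.1):** "Two-sided p-values from the Fisher exact test of the number of subjects with an event will be presented for" a list limited to severe solicited events and serious or severe unsolicited events. Group 5 vs 7 and Group 6 vs 7 are among the contrasts. No effect estimate is mentioned.
- **Six laboratory parameters (6.5.2):** moderate or greater abnormalities with a "two-sided 90% confidence interval using the Miettinen and Nurminen method for the risk difference of each vaccine candidate vs. the comparator group". Group 7 is the comparator for Groups 5 and 6.

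Protocol 10.1.4 says that safety parameters are tabulated and analysed descriptively.

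**The concern.** Groups 5 and 6 against Group 7 are the trial's only randomised comparison of vaccine with a control; the OPV groups are compared with a historical study. Protocol 1.3.1 explains that randomised placebo recipients were added because the phase 1 study had no control group and a relationship of the enzyme changes to vaccine could not be ruled out. One named objective has three components. The laboratory component gets a between-arm estimate with an interval, the two AE components do not, and the SAP gives no reason for the difference.

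Two things are at stake. First, a reader of the planned tables sees two proportions with two separate intervals and has no statement of uncertainty for their difference. Second, SAP section 2 classes analyses not included in the plan as post-hoc and exploratory. An AE contrast added after unblinding would carry that label even though it serves a stated secondary objective.

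**Working it through.** **Inputs from the documents.** IPV group size is 16 to 44 (SAP 3.2, 3.7). Protocol 10.2 sizes Groups 5 to 7 on laboratory elevations: 6% with placebo, 4 × 6% = 24% with vaccine, lower one-sided 95% bound for the risk difference above 0, 80% power at 44 per group. The documents give no AE rates for these groups, so all AE counts below are assumptions.

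**Step 1: reproduce the plan's figure.** I summed exact binomial probabilities over all outcomes with z > 1.645, where z = (p1 − p2) / √[p̄(1 − p̄)(2/n) × 2n/(2n − 1)], the Miettinen-Nurminen statistic at a difference of 0. At n = 44 and 24% vs 6%, power is 79.7%, which agrees with the stated 80%. At n = 16 it is 42.9%. This concerns laboratory elevations, the component that already has a between-arm interval.

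**Step 2: what within-group intervals can hide.** Assume 20/44 on vaccine and 11/44 on placebo.

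- Exact 95% intervals: 20/44 = 45.5% (30.4 to 61.2%); 11/44 = 25.0% (13.2 to 40.3%). They overlap between 30.4% and 40.3%.
- Risk difference: 45.5 − 25.0 = +20.5 points. The Miettinen-Nurminen limits are the values d for which (p1 − p2 − d) / √{[q1(1 − q1)/n1 + q2(1 − q2)/n2] × N/(N − 1)} = ±1.96, with q1 and q2 the maximum-likelihood rates under q1 − q2 = d and N = n1 + n2. The interval is +0.4 to +39.1 points.

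**Step 3: precision the added interval would have.** Two-sided 95% Miettinen-Nurminen intervals, assumed counts:

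| Vaccine vs placebo | Difference | 95% interval (points) |
|---|---|---|
| 22/44 vs 22/44 | 0 | −20.6 to +20.6 |
| 33/44 vs 22/44 | +25.0 | +4.7 to +43.4 |
| 8/16 vs 8/16 | 0 | −33.2 to +33.2 |
| 12/16 vs 8/16 | +25.0 | −9.1 to +54.0 |

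**Step 4: zero events in both arms.** Fisher's p is 1.0 at either size. For 0/n vs 0/n the Miettinen-Nurminen upper limit d solves d/(1 − d) = 1.96² × 2/(2n − 1).

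- n = 44: 7.683/87 = 0.0883, so d = 8.1 points.
- n = 16: 7.683/31 = 0.248, so d = 19.9 points.

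The planned within-group exact upper limit is 1 − 0.025^(1/n): 8.0% at 44 and 20.6% at 16.

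**Step 5: illustrative detection rates, all at two-sided 5%.** Share of trials, by exact enumeration, in which the rule shows a higher vaccine rate:

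| Assumed rates, n per group | Miettinen-Nurminen 95% interval excludes 0 | Fisher p ≤ 0.05 | Exact intervals do not overlap |
|---|---|---|---|
| 24% vs 6%, 44 | 69.6% | 57.8% | 23.6% |
| 24% vs 6%, 16 | 27.4% | 15.0% | 0.8% |
| 60% vs 30%, 44 | 80.5% | 74.2% | 47.8% |

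The 79.7% in step 1 is at one-sided 5% and should not be set against the other two columns. The SAP proposes neither Fisher tests for any-grade AEs nor non-overlap as a rule.

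**The case against.** The protocol announces a descriptive safety analysis, and by-group tables with percentages and exact intervals are a descriptive comparison with placebo. A reader with events and denominators can compute any risk difference. No wrong method is specified, and no AE comparison was used to size the trial. All of this stands, and it keeps the point small. It does not remove it: a risk difference with an interval is also descriptive, the SAP already uses one for laboratory values, and SAP 5.1 promises a comparison.

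Some stronger readings are tempting, but the documents do not support them.

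- **That the secondary objective is never answered.** Its laboratory part has risk differences against placebo, and the AE rates are tabulated by group.
- **That zero severe events would be reported identically at 16 and 44 per group.** Only the p-value is the same. The planned exact intervals would print 0 to 20.6% and 0 to 8.0%, nearly the same contrast as the risk-difference limits.
- **That only any-grade AEs are common enough to inform.** Protocol 1.3.1 reports severe CK elevations in half of the phase 1 participants, and Protocol 11.2 makes laboratory values above grade 1 adverse events automatically. Severe unsolicited events are not shown to be rare, and they have a between-arm test.
- **That the AE comparison falls short of what the trial was sized for.** The 6% vs 24% sizing is for laboratory elevations alone.

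The other side also warns that intervals for every solicited term would produce a long list of unadjusted results. That stands, and the fix is limited to summary categories. It notes too that Group 7 accrues in two stages, so part of it is not concurrent with each candidate. That is true of every planned comparison with Group 7, and this point does not resolve it.

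**Conclusion.** The point holds for the AE part of the IPV secondary safety objective only. For any-grade solicited and unsolicited AEs the SAP specifies no between-arm estimate, interval or test against placebo, despite the commitment in SAP 5.1 and the risk difference given to laboratory values. Serious and severe events have a test without an effect estimate. This is a reporting gap in a secondary safety analysis that is worth closing because it is cheap. It invalidates no stated sample size, alpha or primary conclusion.

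Its size is best seen in precision. If half of each group has an event, the interval for the difference would be about ±21 points at 44 per group and ±33 at 16, and the planned output states neither. The specification gap is read directly from the SAP and needs no assumption. The AE counts, and the 24% vs 6% and 60% vs 30% scenarios when applied to AEs, are illustrations and not rates from the documents.

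**What to change.** In SAP 6.5.2, for Group 5 vs 7 and Group 6 vs 7, post-dose-1, post-dose-2 and overall, add the risk difference with a two-sided 95% Miettinen-Nurminen interval for four categories: any solicited AE, any unsolicited AE, any related unsolicited AE, and any unsolicited AE of grade 2 or higher. The 95% level is the SAP 5.1 default. In SAP 6.5.1, print the same estimate and interval beside the Fisher p-values for these two contrasts. State that all of these are descriptive estimates without multiplicity adjustment.

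The cost is SAP wording and extra table columns, using a method already specified for laboratory values. No new data or subjects are needed. The 6.5.2 addition makes 4 categories × 2 contrasts × 3 periods = 24 nominal intervals. With no true differences and nominal coverage, about 24 × 0.05 = 1.2 would exclude 0 by chance. In 6.5.1 the interval and the Fisher p-value can disagree near the boundary: for 20/44 vs 11/44, Fisher's two-sided p is 0.073 although the interval excludes 0. A sentence saying that the interval is for estimation and is not a second test covers this.

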In general, the safety data were reassuring. There were no remarkable clinical events. The primary clinical endpoints were serious (SAE) and severe adverse events: there were no SAEs; none of the solicited adverse events (pre-specified parameters during the 7 days following vaccination) were severe, and most were mild; and the severe unsolicited AEs were predominantly transient, asymptomatic abnormalities in monitoring laboratory assessments. Most unsolicited clinical AEs were mild, and all self-resolving. No severe AEs were assessed as probably related to the vaccines.

Two participants (one from each cohort) exhibited transient, asymptomatic, severe elevations of AST, both associated with mild or moderate elevation of ALT, severe elevation of CK, no elevation of either GGT or bilirubin, and with complete resolution to normal values. Other AEs on the basis of AST elevations were asymptomatic and generally mild and self-resolving, and also associated with elevated CK levels but normal GGT and bilirubin levels. All AEs on the basis of ALT elevations were transient and asymptomatic, with only one moderate AE and the balance mild. Half of the participants exhibited asymptomatic severe elevations of CK, most often at the day 7 assessment, with resolution of values elevated in the first couple of weeks post-vaccination to normal or close to normal.

Such patterns of enzyme changes have been seen with intermittent, intense exercise, which could provide an explanation for these participants suddenly restricted to a contained unit with an exercise facility for 28 days or more. However, in the absence of a control group in this study, a relationship to vaccine cannot be ruled out. As such, the subsequent study has been redesigned to further assess enzyme changes in additional participants who have not received OPV in the past, and to randomize these participants to receive either one of the vaccine candidates or placebo.

1.3.2 *Potential Benefits*

Subjects who previously completed the childhood polio vaccination schedule and receive a dose of nOPV2 in this study may have a boosted immunity for poliovirus type 2.

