While all safety lab values, including abnormalities, will be summarized, for the specific safety lab parameters listed below, the rate of elevated values will be presented at the subject level overall, by timepoint, by group, and by abnormality grade, and accompanied by a two-sided 90% confidence interval for the risk difference of each vaccine candidate vs. the placebo group.

Safety lab values of OPV-vaccinated subjects will be compared with those of the historical control UAM1 study where possible (e.g. ALT/AST), and in addition, all safety lab values (ALT, AST, CK, GGT, bilirubin and albumin) of OPV-vaccinated subjects and of IPV-vaccinated subjects (Groups 5 and 6) will be compared to the placebo group (Group 7).

Parameters: CPK, ALT, AST, GGT, bilirubin and albumin plus routine other lab. Eventual further testing to include CK subtypes, electrophoresis, auto-antibodies (e.g. ANA, AMA, LKM-1, SLA/LP) and other viral pathogens can be done if any parameter is found to be consistently abnormal.

A listing of subjects with any clinical laboratory test result outside the reference ranges will be provided.

Vital Signs

Pulse rate, SBP, DBP and body temperature will be evaluated by means of descriptive statistics (actual values and changes from baseline and frequency tabulations at each assessment time point and by group).

The percentage of subjects with values beyond clinically important limits (as defined in Appendix 2) will be summarized.

Physical Examination

Abnormal findings in physical examination will be listed.

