10.2 DETERMINATION OF SAMPLE SIZE

Groups 1 through 4:

Sample size is chosen here to mirror that of the historical control study, UAM1. The serotype 2 Day 28 seroprotection rate among OPV-vaccinated individuals is expected to be 95% for subjects receiving a single dose of either investigational vaccine or the type 2 Sabin OPV control vaccine (historical control). 77 evaluable subjects per vaccine group are required to achieve 80% power for a test of non-inferiority to the historical control with a type I error rate of $\alpha = 0.025$ and a non-inferiority margin of 10%. 45 subjects are required to have 90% probability of observing at least one occurrence of an adverse event, when the true adverse event rate is 5%. Allowing for a 10% non-evaluability/dropout rate requires 50 subjects for the safety evaluations. For each vaccine candidate, both 1- and 2-dose groups may be used to assess the Day 28 immunogenicity endpoint, providing 100 subjects for the primary immunogenicity comparison. Therefore, 50 subjects will be allocated to each dose group, to also collect adequate safety data for each group, as defined above.

Groups 5 through 7:

Due to observed transient and asymptomatic elevated values of alanine aminotransferase (ALT), aspartate aminotransferase (AST) and creatine kinase (CK) in the first-in-human phase 1 study, UAM4a, conducted in IPV-vaccinated adults in a contained environment, CK, ALT, AST, GGT, bilirubin and albumin have been designated for further evaluation in this study. Data from OPV-primed individuals in study UAM1 suggest the background rate of spurious elevations with the safe mOPV2 vaccine may be approximately 6%. If the true rate with either candidate vaccine is 4 times the expected rate, 44 subjects per group (each vaccine, plus control) would be required to have 80% power to detect a significant increase in the rate (lower one-sided 95% confidence bound for risk difference > 0) relative to the placebo group. If, upon review of interim safety data, the DSMB agrees that a) despite all reasonable efforts, recruitment has stagnated, and b) sufficient data have accrued to satisfy safety objectives relevant to these groups, group sizes can be truncated.

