6.8 Other Exploratory Endpoints

Deep Sequencing

A separate analysis document will describe the exploratory analyses to be conducted on the sequence of shed virus obtained from one or more stool samples from all volunteers.

Focus will be on retention of attenuating modifications, as well as the potential relationship of sequence change to changes in neurovirulence from vaccine virus to shed virus.

7 Differences from the protocol

Summaries of serum neutralizing antibody fold rise (e.g., GMFR) were not clearly specified in the protocol, and are included in the description of immunogenicity summaries to be computed, in Section 6.6.1.

8 References

[1] Novel Oral Polio Vaccine Product Development: Testing of clinical trial samples by modified mouse neurovirulence test. Viroclinics SOP VC-M140.

[2] Verbeke, G. and Molenberghs, G. (2003), "The Use of Score Tests for Inference on Variance Components," *Biometrics*, 59, 254–262.

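### The SAP changes, without declaring it, which laboratory abnormalities get the 90% interval and which comparator the OPV-vaccinated groups get for the named liver-enzyme and CK risk

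*SAP*

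**What the plan says.** **Protocol, 10.1.4 Safety Data, Clinical Laboratory Tests (same in the synopsis).** For the six named parameters, "the rate of elevated values will be presented at the subject level overall, by timepoint, by group, and by abnormality grade", with a two-sided 90% confidence interval for the risk difference of each candidate against placebo. No grade threshold is set. OPV-vaccinated subjects are compared with UAM1 where possible, with ALT/AST as the example. In addition, the six parameters "of OPV-vaccinated subjects and of IPV-vaccinated subjects (Groups 5 and 6) will be compared to the placebo group (Group 7").

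**Protocol, 10.1.1 Comparative Analyses.** Comparisons are restricted to each vaccine against the UAM1 Sabin 2 control. This does not fit with 10.1.4.

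**Protocol, 10.2.** Groups 5 to 7 are sized on this risk: "the background rate of spurious elevations with the safe mOPV2 vaccine may be approximately 6"%, and "If the true rate with either candidate vaccine is 4 times the expected rate", 44 per group give 80% power for a one-sided 95% lower bound above zero. The grade of elevation is not given.

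**SAP, 6.5.2.** The interval goes with a different rate: "the rate of moderate or greater post-baseline abnormalities will be presented at the subject level overall as well as by timepoint", and also by grade. Groups 5 and 6 are compared with Group 7. For Groups 1 to 4, "comparisons will be made relative to the corresponding UAM1 control (for lab values assessed in both studies").

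**SAP, 6.5.** Recipients are also shown pooled by candidate across priming backgrounds, beside Group 7, as a summary.

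**SAP, 7 Differences from the protocol.** One item is listed: "Summaries of serum neutralizing antibody fold rise (e.g., GMFR) were not clearly specified in the protocol".

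**The concern.** Protocol 1.3.1 explains that, without a control group in phase 1, a vaccine effect on these enzymes could not be ruled out, and that this study was redesigned with a placebo arm for that reason. The interval against a comparator is therefore the analysis that answers the question the redesign was meant to settle.

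The SAP alters that analysis in two ways. First, it raises the threshold. In phase 1 the ALT events were nearly all mild: "All AEs on the basis of ALT elevations were transient and asymptomatic, with only one moderate AE and the balance mild". AST events apart from two severe ones were generally mild. A moderate-or-greater rule leaves most of that ALT/AST pattern outside the headline interval. Second, it removes the placebo contrast for the 200 OPV-vaccinated subjects, who make up most nOPV2 recipients.

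At stake is how a null result would be read. An interval covering zero for moderate-or-greater events could be cited as the outcome of a comparison with 80% power, although the protocol does not say that the power figure applies to that endpoint.

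**Working it through.** **1. The plan's own figure.** Inputs from Protocol 10.2: control rate 6%, candidate rate 4 × 6% = 24%, one-sided α = 0.05, 44 per group. The lower Miettinen-Nurminen bound exceeds zero when

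z = (x/n₁ − y/n₀) / √[ p̄(1 − p̄)(1/n₁ + 1/n₀) · N/(N − 1) ] > 1.645,

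with p̄ = (x + y)/N and N = n₁ + n₀. Power is the sum of Bin(x; n₁, p₁) · Bin(y; n₀, p₀) over all (x, y) that meet this. At 44 vs 44 with 24% vs 6%, power is **79.7%**. The arcsine formula gives n = 2(1.645 + 0.842)²/0.529² = 44.2. The figure of 44 is sound for its inputs. At the permitted minimum of 16 vs 16, the same calculation gives 42.9%.

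**2. Does it carry over to moderate-or-greater?** Only if that endpoint also has a background near 6%. The documents give no background by grade, so the rows below 6% are an assumed range with the 4:1 ratio kept:

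| Background | Candidate | Power at 44 vs 44 |
|---|---|---|
| 6% | 24% | 80% |
| 4% | 16% | 63% |
| 3% | 12% | 53% |
| 2% | 8% | 40% |
| 1% | 4% | 17% |

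**3. CK.** Protocol 1.3.1 reports severe CK elevations in half of the phase 1 participants. These are above the SAP cut. Taking 50% as the candidate rate and keeping 4:1 (again an assumption), 50% vs 12.5% gives 99% power at 44 vs 44 and 76% at 16 vs 16. The threshold is therefore mainly an ALT/AST matter.

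**4. Comparator coverage for OPV subjects.** Safety-lab days, from the secondary endpoints in Protocol 3.2 and the UAM1 synopsis in Appendix 3:

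| Post-baseline day | OPV groups, this study | UAM1 | Group 7 |
|---|---|---|---|
| 7 | Groups 1–4 | yes | yes |
| 14 | Groups 1–4 | **no** | yes |
| 28 | Groups 1–4 | yes | yes |
| 35 | Groups 2, 4 | Group 2 | yes |
| 42 | Groups 2, 4 | **no** | yes |
| 56 | Groups 2, 4 | Group 2 | yes |

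Under the SAP, Days 14 and 42 have no comparative interval for OPV subjects for any of the six parameters, and a parameter that UAM1 did not measure has none on any day. OPV subjects are 200/(200 + 2 × 44) = 69% to 200/(200 + 2 × 16) = 86% of planned nOPV2 recipients.

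**5. What the omitted contrast could show.** With 100 OPV subjects per candidate after dose 1, and 24% vs 6%, power against Group 7 is 88% with 44 placebo subjects and 54% with 16. These figures describe precision only, because the contrast is not randomised.

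**The case against.** The case for leaving the SAP as it is has weight.

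- **Mild values are not lost.** SAP 6.5.2 tabulates every abnormality by parameter, time point and grade, with shift tables, continuous summaries, boxplots and listings. The sentence with the interval also mentions a breakdown by grade. This stands; what remains open is whether any interval covers grade 1.
- **The cut has a basis in the protocol.** Protocol 11.2 treats laboratory values above grade 1 as clinically significant and records them as adverse events. That makes the cut reasonable, but the rule governs event recording and does not redefine the rate in 10.1.4.
- **The protocol disagrees with itself.** Section 10.1.1 limits comparisons to UAM1, and SAP 5.1 follows that for OPV subjects. Section 10.1.4 names no method for the OPV-placebo comparison. The SAP also adds an interval against UAM1 where the protocol promised only descriptive statistics. All true; 10.1.4 is still the specific laboratory rule, and the conflict needs resolving openly.
- **OPV against placebo is not randomised.** It is confounded by priming background, and follow-up differs: Groups 1 and 3 have labs only to Day 28, Group 7 to Day 56. This stands, and any such contrast must be split by dose period. The UAM1 comparison, which the SAP keeps, is not randomised either.

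A reader might go further and infer that most CK data will go untested. That requires UAM1 not to have measured CK. Naming ALT/AST as an example hints at this, but the UAM1 laboratory list is not reproduced. A reader might also put phase 1 event rates into the power formula (AST 2/30, ALT 1/30, ratio 4:1) and conclude that power is 34% and 13%. The documents do not support those as findings: the grade behind the 6% is unstated, the AST count is a floor because further moderate events are not excluded, and nothing fixes the ratio.

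**Conclusion.** The point holds as two undeclared departures from Protocol 10.1.4 on the study's named laboratory risk.

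The endpoint behind the 90% interval is narrowed to moderate-or-greater abnormalities. This matters for ALT and AST, and little for the severe CK elevations. The protocol's 80% power transfers to the narrowed endpoint only if its background is also about 6%; the 63% and 40% at backgrounds of 4% and 2% illustrate sensitivity under an assumed 4:1 ratio and are not estimates.

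The placebo comparison for OPV subjects is reduced to a descriptive display pooled by candidate. The loss at Days 14 and 42 follows directly from the two visit schedules. A loss for CK is possible but cannot be established from these documents.

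The changes may be defensible. They should be stated and justified, and the analyses the protocol promised can be restored from data already being collected.

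**What to change.** In SAP 6.5.2:

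1. Add a row for any-grade post-baseline abnormality (low values for albumin) with its two-sided 90% Miettinen-Nurminen interval. Keep moderate-or-greater as a further row.
2. Add Groups 1+2 and Groups 3+4 against Group 7 for the post-dose-1 period (Days 7, 14 and 28), and Groups 2 and 4 against Group 7 post-dose-2, for all six parameters. Place these beside the UAM1 comparison and label them non-randomised and confounded by priming background.
3. State which of the six parameters UAM1 measured.

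Reconcile Protocol 10.1.1 with 10.1.4. If either departure is kept, list it in SAP section 7 with its reason, and note there that the protocol's 80% power was not calculated for moderate-or-greater events.

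The cost is SAP wording, a protocol clarification and a few more table rows. The drawbacks are that mild elevations add noise and that the OPV-placebo contrast could be over-read if its label is dropped.
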